Appendix 4. Eczema Area and Severity Index (EASI)

The EASI quantifies the severity of a subject's atopic dermatitis based on both severity of lesion clinical signs and the percent of BSA affected. EASI is a composite scoring by the atopic dermatitis clinical evaluator of the degree of erythema, induration/papulation, excoriation, and lichenification (each scored separately) for each of four body regions, with adjustment for the percent of BSA involved for each body region and for the proportion of the body region to the whole body.

Lesion Severity by Clinical Signs: The basic characteristics of atopic dermatitis lesions—erythema, induration/papulation, excoriation, and lichenification—provide a means for assessing the severity of lesions. Assessment of these four main clinical signs is performed separately for four body regions: head and neck, upper limbs, trunk (including axillae and groin) and lower limbs (including buttocks). Average erythema, induration/papulation, excoriation, and lichenification are scored for each body region according to a 4-point scale: 0=absent; 1=mild; 2=moderate; 3=severe. Morphologic descriptors for each clinical sign severity score are shown in the table below.

Clinical Sign Severity Scoring Criteria for the EASI

Score		Description*
Erythema (E)		
0	Absent	None; may have residual discoloration (post-inflammatory hyperpigmentation and/or hypopigmentation).
1	Mild	Light pink to light red
2	Moderate	Red
3	Severe	Deep, dark red
Induration/Papulation (I)		
0	Absent	None
1	Mild	Barely palpable to slight, but definite hard thickened skin and/or papules
2	Moderate	Easily palpable moderate hard thickened skin and/or papules
3	Severe	Severe hard thickened skin and/or papules
Excoriation (Ex)		
0	Absent	None
1	Mild	Slight, but definite linear or picked scratch marks or penetrating surface injury
2	Moderate	Moderate linear or picked scratch marks or penetrating surface injury
3	Severe	Severe linear or picked scratch marks or penetrating surface injury
Lichenification (L)		
0	Absent	None
1	Mild	Barely perceptible to slight, but definite thickened skin, fine skin markings, and lichenoid scale
2	Moderate	Moderate thickened skin, coarse skin markings, and coarse lichenoid scale
3	Severe	Severe thickened skin with very coarse skin markings and lichenoid scale

* The EASI will exclude scalp, palms, and soles from the assessment/scoring.

%BSA with Atopic Dermatitis: The number of handprints of skin afflicted with atopic dermatitis in a body region can be used to determine the extent (%) to which a body region is involved with atopic dermatitis (see table below). When measuring, the handprint unit refers to the size of each individual subject's hand with fingers in a closed position.

Handprint Determination of %BSA

Body Region	Total Number of Handprints in Body Region*	Surface Area of Body Region Equivalent of One Handprint*
Head and Neck	10	10%
Upper Limbs	20	5%
Trunk (including axillae and groin/genitals)	30	3.33%
Lower Limbs (including buttocks)	40	2.5%

Handprint refers to the hand size of each individual subject.

* The number of handprints will be for the entire body region; these values will not be adjusted for exclusion of scalp, palms, and soles from the BSA assessment.

EASI Area Score Criteria

Percent BSA with Atopic Dermatitis in a Body Region	Area Score
0%	0
>0 - <10%	1
10 - <30%	2
30 - <50%	3
50 - <70%	4
70 - <90%	5
90 - 100%	6

Body Region Weighting: Each body region is weighted according to its approximate percentage of the whole body (see table below).

EASI Body Region Weighting

Body Region	Body Region Weighting
Head and Neck	0.1
Upper Limbs	0.2
Trunk (including axillae and groin/genitals)	0.3
Lower Limbs (including buttocks)	0.4

* No adjustment for body regions excluded for assessment.

[figure not shown]
In each body region, the sum of the Clinical Signs Severity Scores for erythema, induration/papulation, excoriation, and lichenification is multiplied by the Area Score and by the Body Region Weighting to provide a body region value, which is then summed across all four body regions resulting in an EASI score as described in Equation below.

[figure not shown]
[figure not shown]
[figure not shown]
[figure not shown]
[figure not shown]
[figure not shown]
[figure not shown]
[figure not shown]
[figure not shown]
$$\text{EASI} = 0.1Ah(Eh+Ih+Exh+Lh) + 0.2Au(Eu+Iu+ExU+Lu) + 0.3At(Et+It+Ext+Lt) + 0.4Al(El+Il+Exl+Ll)$$

A = Area Score; E = erythema; I = induration/papulation; Ex = excoriation; L = lichenification; h = head and neck; u = upper limbs; t = trunk; l = lower limbs.

The EASI score can vary in increments of 0.1 and range from 0.0 to 72.0, with higher scores representing greater severity of atopic dermatitis.

CCI

[figure not shown]

		
		
		
		
		
		
		
		
		
		
		
		
		
		
		
		
		
		
		
		
		
		
		
		
		
[figure not shown]
Very mild	
Mild	
Moderate	
Moderately Severe	
Severe	
Extremely Severe	

15) Compared to the beginning of the study, how would you describe the severity of your skin condition today?

Much better	
Better	
A little better	
No change	
A little worse	
Worse	
Much worse	

CCI

POEM for self-completion

Please circle one response for each of the seven questions below about your eczema. Please leave blank any questions you feel unable to answer.

1. Over the last week, on how many days has your skin been itchy because of your eczema?

No days 1-2 days 3-4 days 5-6 days Every day

2. Over the last week, on how many nights has your sleep been disturbed because of your eczema?

No days 1-2 days 3-4 days 5-6 days Every day

3. Over the last week, on how many days has your skin been bleeding because of your eczema?

No days 1-2 days 3-4 days 5-6 days Every day

4. Over the last week, on how many days has your skin been weeping or oozing clear fluid because of your eczema?

No days 1-2 days 3-4 days 5-6 days Every day

5. Over the last week, on how many days has your skin been cracked because of your eczema?

No days 1-2 days 3-4 days 5-6 days Every day

6. Over the last week, on how many days has your skin been flaking off because of your eczema?

No days 1-2 days 3-4 days 5-6 days Every day

[figure not shown]
[figure not shown]
7. Over the last week, on how many days has your skin felt dry or rough because of your eczema?

No days 1-2 days 3-4 days 5-6 days Every day

Total POEM Score (Maximum 28): _____

© The University of Nottingham

CCI

CHILDREN'S DERMATOLOGY LIFE QUALITY INDEX

The aim of this questionnaire is to measure how much your skin problem has affected you OVER THE LAST WEEK. Please tick ✓ one box for each question.

1. Over the last week, how itchy , "scratchy" , sore or painful has your skin been?	Very much  Quite a lot  Only a little  Not at all 
2. Over the last week, how embarrassed or self conscious , upset or sad have you been because of your skin?	Very much  Quite a lot  Only a little  Not at all 
3. Over the last week, how much has your skin affected your friendships ?	Very much  Quite a lot  Only a little  Not at all 
4. Over the last week, how much have you changed or worn different or special clothes/shoes because of your skin?	Very much  Quite a lot  Only a little  Not at all 
5. Over the last week, how much has your skin trouble affected going out , playing , or doing hobbies ?	Very much  Quite a lot  Only a little  Not at all 
6. Over the last week, how much have you avoided swimming or other sports because of your skin trouble?	Very much  Quite a lot  Only a little  Not at all 
7. Last week , was it school time ? 	If school time: Over the last week, how much did your skin problem affect your school work ? Prevented school  Very much  Quite a lot  Only a little  Not at all 
OR	
was it holiday time ? 	If holiday time: How much over the last week, has your skin problem interfered with your enjoyment of the holiday ? Very much  Quite a lot  Only a little  Not at all 
8. Over the last week, how much trouble have you had because of your skin with other people calling you names , teasing , bullying , asking questions or avoiding you ?	Very much  Quite a lot  Only a little  Not at all 
9. Over the last week, how much has your sleep been affected by your skin problem?	Very much  Quite a lot  Only a little  Not at all 
10. Over the last week, how much of a problem has the treatment for your skin been?	Very much  Quite a lot  Only a little  Not at all 

Please check that you have answered EVERY question. Thank you.

©M.S. Lewis-Jones, A.Y. Finlay, May 1993, This must not be copied without the permission of the authors.

CCI

```
libname c4461001 "/Volumes/app/..... /data_vai" ;  
  
data ps;  
    set c4461001.adps;  
run;  
  
data look;  
    set ps;  
    where param = "EASI02-Total Sum" and viswin ne .;  
    keep subjid param paramn avisit age sex trta viswin visit xviswin aval base chg pchg trtan;  
run;  
  
**example data for a single visit;  
**created from systemic study ;  
**ignore values, only used for illustration;  
  
**data already has one record per subject per visit even if  
**data is missing. Proc Mi needs missing values in order to impute;  
data ex1;  
    set look;  
    where viswin = 9;  
keep subjid dose chg aval base;  
run;  
  
proc means data=ex1;  
    class dose;  
    var chg aval;  
run;  
  
proc sort data=ex1 out=ex2;  
    *data must be sorted before using proc mi;  
    by dose;  
run;  
  
*imputing aval=observed so range of endpoint 0-72 can be included in;  
*mi procedure;  
proc mi data=ex2 seed=1022 n impute=100 out=outimp max=72 min=0;  
    class dose;  
    monotone regpmm(aval= base/details k=5);  
  
    mnar model( aval/modelobs = (dose="0"));  
    var base aval;  
run;  
  
proc univariate data=outimp;  
var aval;  
histogram ;
```

```
run;

data outimp1;
  set outimp;
  chg = aval - base; **calculate chg from baseline;
  pchg=(aval-base)/base*100; **calculate pchg from baseline;
run;
proc sort data = outimp1 out = outimp2;
  by _imputation_ dose subjid;
run;

proc mixed data=outimp2;
  by _imputation_;
  class dose(ref='0');
  model chg = base dose;
  lsmeans dose / diff alpha=.1;
  ods output diffss=diffs lsmeans=lsmeans;
run;

data diffssout;
  set diffss;
  **only keep within contrasts vs placebo;
  where dose = 0;
run;

**now use mianalyze on lsmean differences;
**First sort by group, and _dose (dose = 0 for all groups);
proc sort data=diffssout out=diffssout1;
  by _dose _imputation_;
run;

**now mianalyze by and _dose;
**NB mianalyze only uses estimates and standard errors not CI limits etc. ;
proc mianalyze data=diffssout1 alpha=.1; **specify alpha for 90% CIs here;
  by _dose;
  modeleffects estimate;
  stderr stderr;
  ods output parameter
estimates=parameterestimates;
run;
```

[figure not shown]
CCI

[figure not shown]
CCI

CCI

CCI

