9.4.1. Efficacy Analyses (Part 2 Only)

Endpoint	Statistical Analysis Methods
Secondary (percent change from baseline)	A landmark analysis using analysis of covariance of percent change from baseline in EASI, adjusting for the baseline EASI score, to estimate the effect of the initially randomized treatment in the absence of prohibited medication. The analysis will use the mITT analysis set. Missing data due to any cause including censoring due to initiation of prohibited medication will be imputed using the corresponding vehicle arm, missing data in a vehicle arm will be imputed using data from the vehicle arm assuming data are missing at random (MAR). The analysis will combine the results from the multiple imputations using Rubin's rule's as implemented in SAS PROC MIANALYZE.
CCI	[REDACTED]
[REDACTED]	[REDACTED]

[REDACTED]

[REDACTED]

[REDACTED]

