5.3.2. Efficacy Data

The following patient level data descriptions are also required for defining the pre-specified analyses:

Defined Analysis Data set (at the data level) – endpoint specific	Description
Primary Estimand Continuous Endpoint Set	
This set will include all patients in the mITT population. All data for a subject after the initiation of prohibited medications will be set to missing.
 
Note the primary estimand requires multiple imputation which will be performed on this dataset, the multiple imputations themselves will not be saved in the database, however, the SAS specifications and random number seed will be.

Secondary Estimand Categorical Endpoint Set	
This set will include all patients in the mITT population. All data for a subject after the initiation of prohibited medications, withdrawal of either study drug or the study itself will be set to a failure. Any other additional missing data will be recorded as a failure. Subjects will have either a success or failure in the dataset for all scheduled visits.

Observed Efficacy Set	
This set will include all patients in the mITT population and all observed data and includes all data recorded from the CRF pages. No data will be set to missing or modified from the original CRF record.

The primary analysis will use the primary estimand continuous endpoint set. For each landmark analysis (eg, Cross sectional analysis by week) missing data will be imputed using a control-based imputation method. PROC MI will first be called at the visit and a control-based method (implemented with the missing not at random (MNAR) option) will impute missing vehicle observations under the assumption data are missing at random (MAR) and impute missing treatment observations assuming they are similar to corresponding vehicle patients. Imputation will use the full conditional specification (FCS) method, the imputed data for the treatment and placebo arms will be combined for the analysis.

Summaries of continuous data will use the observed data only and no additional considerations are needed.

Analysis of binary data will use the Secondary Estimand Categorical Endpoint Set. This dataset by definition has no missing data since all missing values will have been set to a failure. Summaries will use the Observed Efficacy Set and will report results on an observed case (OC) basis.

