6.2.1.1. Main Analysis

- Estimand strategy: Estimand E1 ([Section 3.1.2](#)). This estimand is intended to provide an estimate of the treatment effect in the absence of prohibited medication use in a population that may or may not be fully compliant with the treatment.
- Analysis set: mITT ([Section 4](#)) using data prepared in the description of the Primary Estimand Continuous Endpoint Set.
- Analysis methodology: Percent change from baseline will be analyzed using an ANCOVA with the observed (or imputed) Week 6 percentage change from baseline EASI score as the dependent variable with treatment arm and baseline EASI score as the independent variables.
- Intercurrent events and missing data: Data after study drug discontinuation and prohibited medication will be excluded and set to missing. Missing data which will be multiply imputed using a control-based strategy as described in ([Section 5.3.2](#)). Hundred (100) imputed datasets will be used in the analysis and results combined using PROC MIANALYZE.
- The least-squares (LS) means, the 90% confidence interval for the LS means, the difference between the LS means for each pair of treatment groups, and the corresponding 90% confidence interval will be presented for percent change from baseline in EASI score.

CCI

CCI

[figure not shown]450 and \leq 480	>480 and \leq 500	>500
Increase from baseline in QTcF (msec)	>30 and \leq 60	>60	

Categories for PR and QRS

PR (ms)	max. \geq 300	
PR (ms) increase from baseline	Baseline $>$ 200 and max. \geq 25% increase	Baseline \leq 200 and max. \geq 50% increase
QRS (ms)	max. \geq 140	
QRS (ms) increase from baseline	\geq 50% increase	

Categories for Vital Signs

Systolic BP (mm Hg)	min. $<$ 90	
Systolic BP (mm Hg) change from baseline	max. decrease \geq 30	max. increase \geq 30
Diastolic BP (mm Hg)	min. $<$ 50	
Diastolic BP (mm Hg) change from baseline	max. decrease \geq 20	max. increase \geq 20
Supine pulse rate (bpm)	min. $<$ 40	max. $>$ 120

Measurements that fulfill these criteria are to be listed in report.

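### The Week 6 EASI pooling step gives PROC MIANALYZE no complete-data degrees of freedom, so a 21-df ANCOVA is referred to a near-normal cut-off; the effect is small and depends on which arm loses data

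*SAP*

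**What the plan says.** SAP 6.2.1.1 states the main analysis: "Percent change from baseline will be analyzed using an ANCOVA", with treatment arm and baseline EASI as the two terms. On pooling it says "Hundred (100) imputed datasets will be used in the analysis and results combined using PROC MIANALYZE". It asks for LS means, their difference and 90% CIs. Protocol 9.4.1 likewise specifies Rubin's rules through PROC MIANALYZE and mentions no small-sample df.

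The pooling step is written out only in the code for Estimand 1 (SAP Appendix 6). The call is "proc mianalyze data=diffssout1 alpha=.1; specify alpha for 90% CIs here", followed by a `modeleffects` line and "stderr stderr". A comment above it notes that "mianalyze only uses estimates and standard errors not CI limits etc", so the df behind the PROC MIXED limits are not carried forward. `EDF=` does not appear.

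SAP 5.1.2 sets a one-sided alpha of 0.05 and calls the study positive if the null hypothesis is rejected.

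On missing placebo data the documents agree about the assumption. Protocol 9.4.1 has "missing data in a vehicle arm will be imputed using data from the vehicle arm assuming data are missing at random (MAR" and SAP 5.3.2 has "impute missing vehicle observations under the assumption data are missing at random (MAR". They do not agree about the method: SAP 5.3.2 names full conditional specification (FCS), while the code uses a monotone predictive-mean-matching step (`regpmm`, 5 donors).

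**The concern.** Without a complete-data df, the pooling rule treats the within-imputation variance as if it came from a very large sample. Here it comes from 24 participants and three fitted parameters. Using a normal reference in place of a t on 21 df shortens the interval and, unless something offsets it, lets the one-sided test reject too often. This is the only Part 2 endpoint for which the SAP sets a formal decision rule, and it is the basis of the sample size. The choice of df should therefore be fixed before the data are seen.

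**Working it through.** **Inputs.** From SAP 5.1.2: N = 24, 2:1 (16 active, 8 placebo), difference 50, SD 46, one-sided alpha 0.05. From SAP 6.2.1.1: intercept, treatment and baseline, so 24 − 3 = 21 residual df if all 24 are analysed; m = 100.

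**The plan's own figure.** SE = 46 × √(1/16 + 1/8) = 19.92, and 50/19.92 = 2.510. Normal power = Φ(2.510 − 1.645) = 80.7%, which reproduces the stated 80% or so. Noncentral t on 21 df gives 78.3%.

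**Pooled df without `EDF`.** Rubin's df = (m − 1)(1 + 1/r)² = 99/λ², where λ = r/(1 + r) is the fraction of missing information. **With `EDF` = 21**, df = 1/(1/ν + 1/ν_obs), where ν is Rubin's df and ν_obs = (1 − λ) × 21 × 22/24. The documents give no missing-data rate, so λ is an assumed range.

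| λ | df without EDF | cut-off | df with EDF | cut-off |
|---|---|---|---|---|
| near 0 | effectively infinite | 1.645 | 19.25 | 1.728 |
| 10% | 9,900 | 1.645 | 17.3 | 1.738 |
| 20% | 2,475 | 1.6455 | 15.3 | 1.751 |
| 30% | 1,100 | 1.646 | 13.3 | 1.768 |

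With m = 100, Rubin's df cannot fall below 99, so the cut-off never exceeds 1.660. The unpooled 21-df value is 1.7207.

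**Complete-data limit.** P(t₂₁ > 1.645) = 5.74%. Coverage = 1 − 2 × 0.0574 = 88.5%. Half-widths are 1.645 × 19.92 = 32.8 and 1.7207 × 19.92 = 34.3, so the interval is 4.4% too short. With `EDF` = 21 the cut-off is 1.728 and the size 4.93%.

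**With missing values (simulation, percent change).** Assumptions not in the documents: placebo mean −20; baseline EASI mean 26, SD 11 or 5, truncated to 12-72; values missing completely at random; N fixed at 24. SD is 46 and m is 100. Cells have 6,000 to 10,000 trials, with a Monte Carlo SE of about 0.2-0.3 points. Ranges cover the two baseline SDs or repeat runs.

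| Missing | Imputation | Size without EDF | Size with EDF = 21 |
|---|---|---|---|
| 1 placebo | printed PMM | 5.8-5.9% | 4.8-5.0% |
| 2 placebo | printed PMM | 6.2-6.9% | 5.5-5.9% |
| 1 placebo | regression draw | 4.9-5.1% | 4.3% |
| 2 placebo | regression draw | 3.6-5.2% | 4.2% |
| 1 active | printed PMM | 4.3-4.5% | 3.5-3.7% |
| 1 active + 1 placebo | printed PMM | 4.9-5.1% | 3.9-4.3% |
| 2 active + 1 placebo | printed PMM | 3.5-4.0% | 2.9-3.4% |
| 1 at random from 24 | printed PMM | 5.0-5.2% | 4.2-4.3% |
| 2 at random from 24 | printed PMM | 3.9-4.2% | 3.2-3.5% |
| 3 at random from 24 | printed PMM | 3.5-3.8% | 3.0% |

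The regression-draw figures with `EDF` come from a single run; its sizes without `EDF` were 5.1% and 5.2%.

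The printed model step is "model chg = base dose", that is, absolute change and not the percent-change endpoint. The df argument is the same on either scale: on absolute change with one placebo value missing, size is 5.5% without `EDF` and 4.8% with it; with two, 6.3% and 5.2%.

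**The case against.** The strongest objection is that the option often moves size away from 5%. Allocation is 2:1, so a single random missing value is in the active arm with probability 16/24 = 2/3, and two are both placebo with probability only 28/276 = 10%. When active values are imputed from placebo, Rubin's variance is already conservative, and the fix adds to that. This stands. A reader might infer that the planned test is anti-conservative in general; the results do not support that.

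A reader might also put the whole of the 6.2-6.9% for two missing placebo values down to the df. That is not right either: 5.5-5.9% remains with `EDF` = 21, and part of it comes from drawing 5 donors out of only 6 observed placebo values. Under a Bayesian regression draw, which the FCS wording in SAP 5.3.2 allows, placebo-only size is at or near 5% or below without the option.

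Three further points are fair:

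- The 5.74% is a theoretical limit. The documents do not show what the software prints when between-imputation variance is zero.
- Neither SAP 6.2.1.1 nor Appendix 6 asks for a one-sided p-value for EASI. The one-sided test is implied by SAP 5.1.2; the CI is what is explicitly required.
- The code is partly illustrative and needs rewriting anyway, since it models the wrong response. However, its disclaimer concerns the example data values, and the version history says this appendix was revised to agree with Section 6.2. It is the only detailed statement of the pooling.

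Following Rubin's rules as the protocol asks is not an error. The small-sample df is a refinement of them.

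**Conclusion.** The omission is real: a 21-df model is pooled against a cut-off of about 1.645 instead of 1.721. In the complete-data limit the cost is 0.74 points of one-sided size and 1.5 points of CI half-width. With placebo-only missingness, size is about 5.8-6.9% under the printed code, only partly because of the df. With values missing across arms or in the active arm, size is already about 5% or below. The direction therefore depends on who is missing and on which imputation method is used, and the SAP states the method inconsistently.

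Materiality is low. This is a secondary endpoint of a Phase 1 study, and only a borderline result would change. The exact cut-offs assume 24 analysed, and the simulated sizes rest on the assumptions listed with them. The change is still worth making, because it is cheap, settles the df in advance, and keeps size near or below 5% in nearly all the cases examined; the exception is two missing placebo values under the printed PMM.

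**What to change.** 1. In Appendix 6, add `EDF` = participants analysed minus 3 (21 for n = 24) to the PROC MIANALYZE statement.
2. In SAP 6.2.1.1, add one sentence: the pooled CI and test use the small-sample-adjusted df based on that complete-data df, whether or not values are missing.
3. Reconcile the FCS statement in SAP 5.3.2 with the monotone `regpmm` code and state which conditional model is used. In the same revision, make the modelled response match the percent-change endpoint.

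**Cost.** No extra participants. Complete-data power falls from 80.5% (cut-off 1.645) to 78.1% (cut-off 1.728), taking SD 46 as the residual SD; this is still consistent with the plan's approximate 80%. When active values are missing, size moves further below 5% (for example from 5.0% to 4.3% with one value missing at random), and about 3-4 points of power are lost: 72.7% to 69.5% with one active value missing, and 62.8% to 58.6% with two active and one placebo (baseline SD 11).
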